The study is a prospective, randomized, multi-center trial designed to demonstrate the safety and efficacy of the C-Pulse[®] System in relieving heart failure symptoms in patients with ACC/AHA Stage C, NYHA Class III to ambulatory Class IV heart failure. Reduction in heart failure symptoms will be demonstrated by increased freedom from heart failure related hospitalization or death in subjects implanted and treated with the C-Pulse System as compared to a concurrent, randomized control group receiving standard optimal medical therapy (OMT).

Patients will be enrolled into the trial upon providing informed consent. Procedures related directly to the study must not be performed prior to informed consent. Following confirmation of subject eligibility, subjects will be randomized to one of two treatment arms, Treatment or Control, in a 1:1 allocation utilizing a random permuted block design stratified by study center. The Treatment group subjects will receive the C-Pulse[®] System with immediate therapy following implant and OMT while the Control group will continue on OMT. The subjects will not be allowed to cross-over from the assigned group (i.e. a control will not be allowed to receive a C-Pulse). If a treatment subject is explanted, it will be reported in the study analysis per the statistical methods section.

This study will include up to 40 centers in the US and potentially some Canadian centers. The study population will include 388 patients. All subjects who meet eligibility requirements and sign study consent will then be randomized following the baseline testing completion. The follow-up period will be for a minimum of 12 months to assess the safety and efficacy. To facilitate the analysis of the therapeutic effect, it is desired that the system be used all the time. The subject must limit disconnection to a minimal amount of time allowed for personal convenience such as hygiene. The Driver logs subject usage automatically and stores this usage into the system files.

Subjects will be followed for up to five years.

If a subject undergoes anesthesia for the purpose of C-Pulse implantation but does not receive a C-Pulse System, the subject will be followed for 30 days for safety or until they are discharged, whichever occurs first.

[figure not shown]

Figure 1. Study Design Flowchart

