In the event the subject becomes lost to follow-up, the investigational site should make two documented attempts to contact the subject. A Study Exit record must be completed and the subject will no longer be followed in the clinical study.

Data Collection Overview

A review of patient files is required to determine preliminary eligibility according to patient inclusion and exclusion criteria. Baseline data including functional tests must be collected no more than **30** days prior to randomization. Baseline imaging such as echo and CT scans must be collected no more than 90 days prior to randomization. See the data collection table for details.

Follow-up data will be collected at the time of implant, hospital discharge, at planned follow-ups (6 week, 3, 6, 12, 18-month and annually from the implant date thereafter up to 5 years). All serious adverse events will be collected throughout the study until closure.

All study subjects will follow the prescribed follow-up scheduled despite randomization. Day 0 for the treatment group will be the day of implant. Day 0 for the Control Group will be the day of randomization. Each group will continue with optimal medical therapy for the duration of the study, including all standard of care medications and treatments including transplant, VAD, etc. If the subjects are transplanted or placed on another device they will be censored from the primary endpoint analysis and study exited. Subjects implanted with the C-Pulse will be followed until device removal. If the PIL is explanted and not replaced, the subject will be followed for safety until removal of the entire system.

Data will be collected via electronic data capture (EDC) screens referred to as e-case report forms (eCRFs). Echocardiogram tapes and digital storage media must be documented in the patient medical record for source documentation.

Table 1, below outlines the data collection with the appropriate follow-up time windows.

Table 1. Follow-up Windows

Evaluation	Time Window
Pre-Implant Evaluation	No more than 30 days prior to implant
Randomization	Post Baseline Testing and Pre-Implant
Implant	Day 0 (Treatment Group) – Implant Day 0 (Control Group) – Randomization
Pre-Discharge	Within 36 hours prior to discharge
6 – week follow-up	Days 42 ± 7 Post-Implant
3 – month follow-up	Days 90 ± 14 Post-Implant
6 – month follow-up	Days 180 ± 30 Post-Implant
12 – month follow-up	Day 365 ± 30 Post-Implant
18 – month follow-up	Day 540 ± 30 Post-Implant

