All cardiac medications (including diuretics) will be recorded on the Medication eCRF. Doses are required for all cardiac medications including diuretics.

Data will be completed on the eCRFs. The medical record will be used for source documentation.

Clinical Procedures – Pre-implant through discharge

The hospitalization phase is divided into three major parts: (i) Prior to implant, (ii) Implant procedures, and (iii) Post-implant to discharge.

Pre-Implant Considerations

Medication therapy

Prescribed drugs are to be maintained until the time of surgery unless instructed otherwise by the anesthetist. Prophylactic anti-coagulation should be stopped. Pre-medications should be given in accordance with institutional protocol.

Cardiac Resynchronization Therapy (CRT)

Per the eligibility criteria a patient should not be enrolled earlier than 90 days following CRT implant. Patients enrolled with a CRT device must have the Cardiac Resynchronization Therapy continued during the follow up period. ICD therapy should remain activated except during the surgical implantation.

Planning for Device and Percutaneous Tube Positioning

Percutaneous Interface Lead exit site should be identified prior to surgery. Pay particular attention to the costal margins, belt line, and impact of sitting and standing and lying, and the exit site when wearing the Driver. The distance of the exit site from the costal margin should be considered in relation to the thickness of subcutaneous tissue in order to prevent the percutaneous tube from rubbing against the costal margin. Also consider patients who inject insulin into the abdominal area. Mark the exit site.

Antisepsis Prophylaxis

Please refer to the Infection Control Guidelines in the Appendices.

Implant Considerations

Implantation of the C-Pulse System will only occur with personnel trained by Sunshine Heart Inc. personnel or designees.

Note: Refer to the Instructions for Use (IFU) for the C-Pulse® Cuff, Percutaneous Interface Lead, Driver, Tunneler, C-Patch™ and C–Pulse® System which outline device preparation, implantation, and operation.

Post-Implant Considerations (prior to discharge)

1. Patient taken to ICU – driver may be disconnected for transport.
2. Extubate patient, when appropriate – move to the telemetry ward when appropriate.
3. Ensure both Drivers are configured with the same settings and verify function of both as above – optimizing settings occurs day 1-3 post-op.

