The improvement in 6 Minute Hall Walk will be computed as the difference between the baseline and follow-up value at 18 months. Subjects not evaluated at 18 months due to prior VAD implant, heart transplant or death will have the worst possible outcome imputed for improvement. Subjects unable to perform the 6MHW will have a value of 0 for the 18 month result. Improvement at 18 months will be compared between treatment groups under the following hypotheses.

Hypotheses

$$H_0: DT = D_c$$

$$H_A: DT \neq D_c,$$

where DT represents the distribution of improvement in 6MHW for the Treatment and D_c the distribution of improvement in 6MHW for Control. Details of the analysis methods can be found in the Statistical Analysis Plan.

3. Improvement in LVEF at 12 months

The improvement in LVEF will be computed as the difference between the baseline and follow-up values at 12 months. Subjects not evaluated at 12 months due to prior VAD implant, heart transplant or death will have the worst possible outcome imputed for improvement. Improvement at 12 months will be compared between treatment groups under the following hypotheses.

Hypotheses

$$H_0: DT = D_c$$

$$H_A: DT \neq D_c,$$

where DT represents the distribution of improvement in LVEF for Treatment and D_c the distribution of improvement in LVEF for Control. Details of the analysis methods can be found in the Statistical Analysis Plan.

4. Days Alive and Out of Hospital due to Worsening Heart Failure through 12 Months

The total days alive and out of hospital due to worsening heart failure following randomization through 12 months will be computed for each subject in a similar fashion to DAOH except hospitalization days for reasons other than heart failure will not be subtracted from the total possible days. The treatment groups will be compared under the following hypotheses.

Hypotheses

$$H_0: DT = D_c$$

$$H_A: DT \neq D_c,$$

where DT represents the distribution of days alive and out of hospital due to worsening heart failure for Treatment and D_c the distribution of days alive and out of hospital due to worsening heart failure for Control. Details of the analysis methods can be found in the Statistical Analysis Plan.

5. Days Alive and Out of Hospital through 12 Months

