The total days alive and out of hospital following randomization through 12 months will be computed for each subject. Each subject will contribute a maximum of 365 days alive and outside of hospital following randomization. Days the subject is in hospital will be subtracted from the maximum. For subjects with a death or study exit prior to 12 months, the days from the date of death or study exit to the date at 365 days post randomization will be subtracted from the total. The treatment groups will be compared under the following hypotheses.

Hypotheses:

$$H_0: DT = D_c$$

$$H_A: DT \neq D_c,$$

where DT represents the distribution of days alive and out of hospital for Treatment and D_c the distribution of days alive and out of hospital for Control. Details of the analysis methods can be found in the Statistical Analysis Plan.

6. Improvement in KCCQ Score at 12 months

The improvement in overall KCCQ score will be computed as the difference between the baseline and follow-up scores at 12 months. Subjects not evaluated at 12 months due to prior VAD implant, heart transplant or death will have the worst possible outcome imputed for improvement. Improvement at 12 months will be compared between treatment groups under the following hypotheses.

Hypotheses

$$H_0: DT = Dc$$

$$H_A: DT \neq Dc,$$

where DT represents the distribution of improvement in Overall KCCQ Score for Treatment and Dc the distribution of improvement in Overall KCCQ for Control. Details of the analysis methods can be found in the Statistical Analysis Plan.

Additional Supportive Analyses

1. Components of primary efficacy endpoint

The components of the primary endpoint will be summarized individually by treatment group. The proportions of subjects with heart failure related hospitalization, LVAD implant, heart transplant, and death due to worsening heart failure will be reported and the time to each event will be described by Kaplan-Meier curves. The number and proportion of subjects with hospitalization due to worsening heart failure as well as the rate per patient year will be summarized.

2. All-cause mortality

All-cause mortality will be summarized by treatment group by number and percent of subjects as well as by Kaplan-Meier curves.

3. Major cardiac events

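### Both secondary endpoints on days alive and out of hospital score a subject who leaves the study alive as dead from the exit date

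*Combined protocol and SAP*

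**What the plan says.** Under Secondary Efficacy Endpoints, item 5 (DAOH through 12 months) starts each subject at 365 days from randomization. It then states: "Days the subject is in hospital will be subtracted from the maximum". The next sentence begins "For subjects with a death or study exit prior to 12 months, the days from the date of death or study exit" and removes everything from that date to day 365, with no distinction between dying and leaving. Item 4 (the worsening-heart-failure version) is computed "in a similar fashion to DAOH except hospitalization days for reasons other than heart failure", which are not subtracted. That is its only stated exception, so it carries the same exit rule.

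Subject Withdrawal or Loss to Follow-Up says of both situations: "A Study Exit record must be completed and the subject will no longer be followed in the clinical study". Data Collection Overview adds: "If the subjects are transplanted or placed on another device they will be censored from the primary endpoint analysis and study exited".

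Two further ends of follow-up occur only in the device arm. One is in Data Collection Overview: "Subjects implanted with the C-Pulse will be followed until device removal". The other is in Design, for a subject anesthetized but not implanted: "the subject will be followed for 30 days for safety or until they are discharged, whichever occurs first". The protocol does not say whether either is a study exit for DAOH.

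The other secondary endpoints (six-minute walk at 12 and 18 months, LVEF, KCCQ) impute the worst outcome when the visit was missed because of an earlier VAD, transplant or death. They do not do so for live withdrawal or loss. Under Handling of Missing Data, the primary analysis censors losses and explants at the last assessment. The paragraph after it plans missing-data analyses for KCCQ, six-minute walk and LVEF, and closes with a general promise of multiple imputation to test the study results against loss to follow-up.

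**The concern.** A subject who withdraws on day 60 and lives through the year receives the same score as one who died on day 60. Two of the six hierarchical secondary tests use this scoring. It departs from how the plan treats live loss elsewhere, although for transplant and VAD the endpoints agree.

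The trial cannot conceal assignment, because one arm is implanted and the other continues medical therapy. Reasons for leaving may therefore differ by arm. If they do, the difference in exits enters the endpoint as a difference in days alive, whether or not the device does anything.

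**Working it through.** **The plan's own figure.** The plan claims an overall Type I error of 5% for the secondaries. In a fixed sequence, each test is run at 0.05 only after all earlier ones have rejected, so the overall error is at most 0.05 provided each test is itself valid. The 5% is reproduced on that condition. The question is whether the exit rule keeps the DAOH tests valid.

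**Inputs from the protocol.** 388 subjects, 194 per arm; 10% attrition per year (Primary Efficacy Endpoint Sample Size); 84% six-month freedom from all-cause mortality in the reference study (Justification section). At constant hazard the last gives 12-month mortality of 1 − 0.84² = 29.4%.

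**Assumed inputs.** A lower mortality of 16%; exit uniform over the year and unrelated to outcome; 28% of subjects with heart-failure hospital days (1 day plus a gamma, mean 13 days); two-sided rank-sum test at 0.05.

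**Days removed.** If all attrition is live exit, 10% × 194 = 19.4 subjects per arm leave within 12 months.
- Per randomized subject the rule removes 0.10 × 182.5 = 18.3 days (18.6 with exponential exit).
- With death competing, this falls to 16.1 days at 16% mortality and 14.4 days at 29.4%.

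**Difference created by unequal exit.** It is approximately (difference in exit proportion) × 182.5, scaled by 16.1/18.3 = 0.88 or 14.4/18.3 = 0.79 for competing death. A 5-point gap gives 9.1 × 0.88 = 8.0 or 9.1 × 0.79 = 7.2 days. A 10-point gap gives 16.1 or 14.4 days.

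**Null simulation, endpoint 4** (no true effect, 4,000 trials per scenario; results at 16% / 29.4% mortality; difference is device minus control):

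| Exit, device v control | Rejections | Mean difference (days) |
|---|---|---|
| 10% v 10% | 4.4% / 5.3% | +0.2 / +0.1 |
| 5% v 10% | 12.0% / 10.1% | +8.1 / +7.1 |
| 10% v 5% | 12.6% / 10.0% | −8.2 / −7.4 |
| 5% v 15% | 34.7% / 23.9% | +16.3 / +14.4 |
| 15% v 5% | 34.2% / 24.6% | −16.2 / −14.5 |

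- Modest gaps of 8% v 10% or 10% v 12% give about 5 to 6.5% rejections and about 3 days.
- A repeat run of 5% v 10% at the higher mortality gave 9.1%, hence the range of 9 to 13%.
- Scoring true days without the exit rule, 5% v 15% gives 5.3% / 4.7%.
- A second model (heart-failure admissions from the plan's 0.72 at six months, 7-day mean stay, six-month survival 0.84 or 0.92) gives 23.8% to 32.0% at 5% v 15%, and 4.7% to 5.3% with full days observed.

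**Endpoint 5.** I quote no false-positive rate. Clinical Procedures says "The hospitalization phase is divided into three major parts: (i) Prior to implant, (ii) Implant procedures, and (iii) Post-implant to discharge", and endpoint 5 subtracts all hospital days, so the implant stay lowers the device arm's score. At 5% v 10% exit, the mean difference is +2.8 / +2.1 days with an assumed 5-day stay and −2.1 / −2.6 days with 10 days.

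**Check of the remedy.** Within-arm hot-deck imputation with 5 draws, Rubin's rules on the mean difference, 1,000 trials per scenario; exit 5% v 10%, 5% v 15% and 15% v 5%, at both mortalities. Error against true days:

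| Death hazard after exit | Imputation | Current rule |
|---|---|---|
| unchanged | under 0.1 days | 7.1–16.0 days |
| doubled | 0.4–1.5 days | 6.4–15.2 days |
| quadrupled | 1.2–3.8 days | 5.2–13.6 days |

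Rejections were 4.0–6.3% with imputation and 10–36% under the current rule.

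**The case against.** **The imputation promise may already cover this.** The closing sentence of Handling of Missing Data speaks of the study results in general. It does not clearly reach DAOH, for two reasons: it sits in the paragraph on KCCQ, six-minute walk and LVEF, and under the item 5 rule an exited subject already has a complete DAOH value, so nothing is missing to impute. The protocol also defers analysis methods to the Statistical Analysis Plan. A DAOH sensitivity analysis there would help, but the scoring rule itself is stated in the protocol and would still apply.

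**The harm is conditional.** This stands. The plan gives one attrition rate, and no passage supports a twofold or threefold difference between arms. With small gaps the effect is slight. The rejection rates are marginal rates for the fourth test in a sequence, reached only after the primary and three earlier secondaries succeed.

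**Ten percent is probably high for live exit.** This also stands. The sample-size justification treats half of deaths as not due to worsening heart failure, so planned attrition may include such deaths, and it may include explants. The 14 to 19 days is an upper figure.

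**DAOH needs a value for everyone.** True: censoring, as in the primary analysis, cannot simply be carried over. A prespecified worst-case score is defensible as a sensitivity analysis, but as the main analysis it equates leaving with death.

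**Stronger readings.** A reader might infer that the rule favors the device or that the trial's overall error rate is inflated. The documents support neither: the direction follows whichever arm has fewer exits, and equal exit leaves the error near 5%. A reader might also take device removal or failed implantation as a study exit, so that a subject last followed on day 30 loses 365 − 30 = 335 days. The protocol does not say so; it leaves the point open. Finally, the two statements of the gate for secondary testing might look like a Type I error problem. Secondary Efficacy Endpoints requires both primary objectives; Type I Error Control names efficacy only. Following the stricter one satisfies both, and error is held either way.

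**Conclusion.** The point holds as a scoring defect in two secondary endpoints and should be corrected. Followed as written, the plan scores subjects who leave alive as dead from the exit date.

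The size depends on exit. If it is equal, days are understated in both arms by at most about 14 to 19 per subject, with no inflation of error. If it is unequal, the bias runs toward the arm with fewer exits: about 3 days for a 2-point gap, 7 to 8 days at 5% v 10%, and 14 to 16 days at 5% v 15%. The corresponding rejection rates for endpoint 4 are about 5 to 6.5%, 9 to 13%, and 24 to 35%. They rest on assumed imbalances, an assumed rank-sum test, assumed hospital-day and mortality inputs, and exit unrelated to outcome. The reading of the text is firm; the size of harm in this trial cannot be known from the documents.

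**What to change.** In items 4 and 5 of Secondary Efficacy Endpoints:
- Subtract all post-exit days only for death, and for LVAD or transplant if the sponsor states so.
- For live withdrawal or loss to follow-up, multiply impute the unobserved days as the main analysis.
- State how device removal and failed implantation are scored in DAOH.
- Report exits by arm and reason.
- Keep the current rule as a sensitivity analysis.

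Under Handling of Missing Data, name DAOH among the endpoints covered.

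The cost is wording and minor programming, with no added subjects or visits. The downside is that imputation assumes exit is missing at random. The main and sensitivity analyses bracket the truth only if subjects who exit do no better afterwards than those who stay; if they do better, both understate their days.

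Two editorial corrections can go in with it. Align the gate in Type I Error Control for Secondary Objectives with Secondary Efficacy Endpoints, so that both primary objectives must be met. In Handling of Missing Data, replace the signed-rank test, which is for paired or one-sample data, with the Wilcoxon rank-sum test, since the stated purpose is to compare the arms.

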There is no published study using the same endpoint in a similar heart failure treatment population. The MEDAMACS study has an enrollment population similar to the target population for the C-Pulse System Pivotal Trial and has an endpoint close to the C-Pulse System primary endpoint except that all-cause mortality is included. The study reports a 6-month survival free from LVAD implant, heart transplant or inotrope use of 64%. As this likely represents a higher event probability than the C-Pulse System primary endpoint, a higher freedom from event at 6 months was calculated assuming half the mortality events were not due to worsening heart failure. As the 6 month freedom from all-cause mortality estimate was 84%, an estimate for freedom from worsening heart failure event of 72% is chosen for the Control group estimate. The current proposed study was therefore powered to detect a 30% reduction in the probability of worsening heart failure event (an assumed hazard ratio of 0.70). The C-Pulse System Feasibility Study has an estimated freedom from worsening heart failure event of 95.0% at 6 months and 72.4% at 12 months, however, as this is based on 20 subjects the confidence limits of the estimate are wide and it is therefore not a desirable estimate on which to entirely base the sample size assumptions.

The study is powered to detect a statistically significant difference in freedom from worsening heart failure events favoring Treatment over Control. Worsening heart failure events represent an objective measure of worsening heart failure and an observed reduction would represent a clinically significant and meaningful improvement in heart failure subjects' health. The planned secondary analyses will provide supporting evidence of superiority in the improvement of QOL and other clinical parameters demonstrating the effectiveness of C-Pulse therapy in relieving heart failure related symptoms and associated morbidity.

Primary Safety Endpoint

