The proportions of subjects within each randomization group with major cardiac events (myocardial infarction, heart failure and stroke) and the composite of major cardiac events or death will be computed. Ninety-five percent binomial exact confidence limits will be calculated and time to each of these endpoints will be described by Kaplan-Meier curves.

4. Adverse events

The frequency and rate (based on the Poisson distribution) of all adverse events will be summarized for each randomization group overall and by seriousness, severity, relatedness and expectedness. Differences in the incidence of adverse event rates will be compared between randomization groups using Poisson regression. Ninety five percent (95%) confidence intervals (based on the Poisson distribution) for the risk ratios will be computed. The number and proportion of subjects with adverse events well as the rate per patient year will be summarized.

5. Quality of life

Quality of life and changes from baseline as measured by the MLWHF and KCCQ assessments will be summarized by treatment group.

6. Device Performance and Usage

The device performance and subject usage will be summarized. The exchange of implanted components that did not result in a device malfunction adverse event will be reported. Device usage will be summarized as the percent of follow-up time with device use. This will be summarized as both a continuous outcome and in quartiles of use defined as 0-25%, 26-50%, 51-75% and 76-100%. The impact of device usage on the primary and secondary efficacy outcomes will be assessed within the C-Pulse arm by summarizing outcomes by quartile of use.

7. Reduction of diuretics

The dose of diuretics pre-implant and during support will be summarized for control and treatment groups.

8. ICD discharges

The frequency of ICD discharges will be summarized for control and treatment groups.

9. Summary of outcomes – Transplant, VAD Implantation, Recovery or Death

A competing outcomes summary will be completed demonstrating the occurrence of time to transplant, VAD implantation, Recovery or Death. Recovery will be defined as NYHA Class I/II and an Ejection Fraction greater than 40%. The data will be summarized for both the control and treatment groups.

Assessment of Poolability

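### Kaplan-Meier curves for HF hospitalization, HF death, MI and stroke, read as incidence, overstate these components because competing death and study exit are not accounted for

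*Combined protocol and SAP*

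**What the plan says.** All the relevant text is in the combined document, mostly under Statistical Methods and Data Analysis, Additional Supportive Analyses.

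- **Item 1 (components of the primary efficacy endpoint).** "The proportions of subjects with heart failure related hospitalization, LVAD implant, heart transplant, and death due to worsening heart failure will be reported". For timing, the same sentence prescribes one method for all four components: "the time to each event will be described by Kaplan-Meier curves". Only death due to worsening HF is a component here; all-cause mortality is item 2.
- **Item 3 (major cardiac events).** Proportions of subjects with "major cardiac events (myocardial infarction, heart failure and stroke) and the composite of major cardiac events or death will be computed", and "time to each of these endpoints will be described by Kaplan-Meier curves".
- **Item 9 (summary of outcomes).** "A competing outcomes summary will be completed demonstrating the occurrence of time to transplant, VAD implantation, Recovery or Death", for both arms. No estimator is named, and HF hospitalization, HF death, MI and stroke are not included.
- **Data Collection Overview.** "If the subjects are transplanted or placed on another device they will be censored from the primary endpoint analysis and study exited".

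Items 1 and 3 do not say how death, LVAD or transplant enters the curves. The primary and secondary endpoint sections refer to a separate Statistical Analysis Plan for details; items 1 and 3 carry no such reference.

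**The concern.** A subject who has died cannot later be hospitalized or have an MI or stroke, and a subject who dies of another cause cannot die of HF. A Kaplan-Meier curve for one such event normally censors the subject at the competing death. One minus the curve then estimates the risk in a hypothetical setting without competing deaths, not the proportion of subjects who actually have the event. Exit at LVAD or transplant adds to the effect: later events are not observed, and these subjects are unlikely to resemble those who stay.

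These displays are where a reader would look to see which component drives the composite result. Curves that are too high misstate how often each component occurs, and they can disagree with the crude proportions reported beside them. The size of the excess depends on competing mortality, which may differ between an arm that has thoracic surgery and one that does not.

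**Working it through.** **The plan's own figure.** The documents give no incidence for any single component. The only figure that separates HF from non-HF death is the control-arm rate in the justification of the efficacy sample size: "As the 6 month freedom from all-cause mortality estimate was 84%, an estimate for freedom from worsening heart failure event of 72% is chosen". The reference study's six-month event-free proportion is 64%, and half of its deaths are assumed not due to worsening HF. So 0.64 + 0.5 × (1 − 0.84) = 0.72, which reproduces exactly.

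**Hazards per year, assumed constant.**
- All-cause death: −ln(0.84)/0.5 = 0.349.
- HF death and non-HF death: half each, 0.174.
- Any worsening HF event: −ln(0.72)/0.5 = 0.657.
- LVAD or transplant combined, L: not in the documents; assumed 0 to 0.30.
- First HF hospitalization: 0.657 − 0.174 − L = 0.483 − L. This assumes that the HF-death hazard applies to first events.
- MI or stroke: not in the documents; assumed 0.05.

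**Formulas.** For an event with hazard h and competing hazard c at t years:
- one minus Kaplan-Meier = 1 − exp(−h·t)
- cumulative incidence = h/(h + c) × [1 − exp(−(h + c)·t)]

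**Results at 12 months.**

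| Component | h | c | 1 − KM | Cumulative incidence | Excess (points) |
|---|---|---|---|---|---|
| First HF hospitalization, L = 0 | 0.483 | 0.349 | 38.3% | 32.8% | 5.5 |
| First HF hospitalization, L = 0.10 | 0.383 | 0.449 | 31.8% | 26.0% | 5.8 |
| First HF hospitalization, L = 0.30 | 0.183 | 0.649 | 16.7% | 12.4% | 4.3 |
| HF death, L = 0 | 0.174 | 0.174 | 16.0% | 14.7% | 1.3 |
| HF death, L = 0.30 | 0.174 | 0.474 | 16.0% | 12.8% | 3.2 |
| MI or stroke, L = 0 | 0.05 | 0.349 | 4.9% | 4.1% | 0.8 |
| MI or stroke, L = 0.30 | 0.05 | 0.649 | 4.9% | 3.6% | 1.3 |

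In relative terms the excess is 17% to 35% for first HF hospitalization and 9% to 25% for HF death.

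**Growth with time.** For HF death at 24 months, 29.4% compares with 25.1% (L = 0) to 19.5% (L = 0.30), an excess of 4.3 to 9.9 points. At five years, the planned maximum follow-up, it is 58.2% against 41.3% even with L = 0.

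**LVAD and transplant.** Suppose each has a hazard of 0.15 and competes with the other and with death (c = 0.349 + 0.15 = 0.499). Each then reads 13.9% by Kaplan-Meier at 12 months, against 0.15/0.649 × [1 − exp(−0.649)] = 11.0%. Item 1 and item 9 could therefore give different pictures of the same events.

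**Lower competing risk.** With c = 0.10 and h = 0.30, the 12-month figures are 25.9% and 24.7%, a gap of only 1.2 points.

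**The case against.** The strongest reply has four parts.

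- **The plan already recognizes competing outcomes.** Item 9 does so for transplant and VAD in both arms. A reader might infer that every component has been left without such an analysis; item 9 shows otherwise. What stands is that it names no estimator and omits HF hospitalization, HF death, MI and stroke.
- **Censoring is inferred.** The Data Collection Overview sentence concerns the primary analysis, and no text says that these curves will be read as incidence. That is true. It is nevertheless the ordinary meaning of a Kaplan-Meier curve for one event type, and the exit rule ends observation whatever the analysis. If the separate Statistical Analysis Plan, which is not in the text available here, already settles this, the point falls away.
- **Other summaries exist.** Crude proportions, HF hospitalization rates per patient-year, all-cause mortality and a composite with death are all planned. They limit the harm but do not correct the curves.
- **The alternative is not neutral.** Cumulative incidence also depends on competing mortality. With a hospitalization hazard of 0.483 in both arms and competing hazards of 0.349 and 0.175, both Kaplan-Meier curves read 38.3% at 12 months, while actual incidence is 32.8% and 35.4%. Neither display alone isolates a treatment effect on one component.

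Three stronger readings are tempting and are not supported. One is that component curves adding up to more than the composite would prove the bias. One subject can be hospitalized, receive an LVAD and later die, so correct curves can also exceed the composite in sum. The second is that LVAD or transplant prevents every other event; an LVAD does not prevent a stroke or a death, and it is study exit that ends observation. The third is to size the bias from the reference study's 36% events (100 − 64), less 16 points of death. The remaining 20 points are LVAD, transplant and inotrope use, so they say nothing about hospitalization, MI or stroke.

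**Conclusion.** The concern holds for HF hospitalization, HF death, MI and stroke in items 1 and 3. The named method, read as incidence, overstates them, and no competing-risk estimate is planned for them. The illustrative 12-month excess is 4.3 to 5.8 points for first HF hospitalization, 1.3 to 3.2 points for HF death and about 1 point for a rare event.

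These sizes rest on constant hazards, on the reference-study figures used in the plan, and on assumed hazards for LVAD/transplant and for rare events. The later figures are the least secure. Six-month survival of 84% held constant gives 0.84⁴, or about 50%, at two years, although the eligibility criteria exclude patients expected to survive less than two years. If mortality in the trial is lower, the excess is smaller.

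A reader might infer that the primary result is biased. The documents do not support that: these are descriptive supportive displays, and the primary test, type I error and sample size do not depend on them. This is a worthwhile improvement in reporting rather than a flaw in the trial's main inference.

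**What to change.** Amend items 1, 3 and 9 as follows.

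- For HF hospitalization, HF death, MI and stroke, replace Kaplan-Meier with Aalen-Johansen cumulative incidence curves by arm.
- State the competing events for each curve: death (non-HF death for the HF-death curve), and LVAD or transplant with study exit. For MI, stroke and HF death, say explicitly that treating LVAD or transplant as competing is a choice that follows from the exit rule.
- Name the same estimator for LVAD and transplant in items 1 and 9, so that the two displays agree.
- Keep Kaplan-Meier for all-cause mortality and for composites that include death. State whether vital status is known after exit at LVAD or transplant, since otherwise those curves are censored there too.
- Present the cumulative incidence curves beside the mortality curves and the planned event rates, because they also move with competing mortality.

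The cost is a few sentences and standard software. No sample-size change is needed, and the curves themselves need no new data.
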